9.2 Visit description - *amended*

This section was changed in Amendment 3, see Section 15.1.2.14.

One month in the study schedule corresponds to 30 days. Although study visits should occur as close as possible to the time points specified in the protocol, a time frame of ± 7 days is allowed for Visit 2 (Month 1), and for the Up-titration Visit(s). Starting from Visit 3 (Month 4), a time frame of ± 12 days is allowed for all regular visits.

All procedures and assessments should preferably be conducted **on the day of the visit**; however, if this is not possible for logistical reasons, the following time windows are allowed:

Blood sampling, ECG and recording of vital signs:

- Screening Visit and all visits starting from Visit 2: Visit date ± 7 days
- Run-In, PD and EOS Visit: Visit date ± 3 days

Sub-studies / iohexol and biomarker samples:

- all visits starting from Visit 3: Visit date ± 7 days
- PD and EOS Visit: Visit date ± 3 days

Sub-study / echocardiography (note that each time an echocardiography is performed, one blood sample should be drawn to assess the echo biomarkers):

- at Visit 1: Visit date -14 / +7 days
- Other visits: Visit date ± 30 days

NOTE: If applicable, a subject who is not eligible at the Run-in or Screening Visit may be re-screened at a later time (see Section 6.4.2.1) or switch over to Study 16244 (see Section 6.4.2.2) provided the pre-requisites are met.

9.2.1 Run-in Visit (4 to 16 weeks prior to the Screening Visit) - *amended*

This section was changed in Amendment 3, see Section 15.1.2.15.

The following procedures and assessments will be performed at the Run-in Visit:

- Obtain signed informed consent (may be done earlier).
NOTE: any study-specific procedure can be performed only if written informed consent is **available**
- Check inclusion and exclusion criteria (see Sections 6.1 and 6.2)
- Collect demographic data, smoking status and alcohol consumption (see Section 9.3.1)
- Record medical history (see Section 9.3.2)
- Record use of prior and concomitant medication (see Section 8.1)
- Perform physical examination (see Section 9.7.3)

- Record body weight, height, waist and hip circumference (see Section 9.7.4)
- Record vital signs (see Section 9.7.5)
- Perform 12-lead ECG (see Section 9.7.6)
- Take samples (hematology, HbA_{1c}, chemistry and urinalysis) for central laboratory evaluations (see Section 9.7.2.1).
Note: If HbA_{1c} cannot be analysed by the central laboratory due to technical reasons, subject can be considered suitable for randomization with one result only (Run-In or Screening).
- Record adverse events (see Section 9.6.1), accounting for the rules of assessment and documentation (see Section 9.6.1.3)

9.2.2 Screening Visit (≤ 2 weeks prior to Visit 1) - *amended*

This section was changed in Amendment 3, see Section 15.1.2.16.

The following procedures and assessments will be performed at the Screening Visit:

- Check inclusion and exclusion criteria (see Sections 6.1 and 6.2)
- Record use of concomitant medication (see Section 8.1)
- Perform physical examination (see Section 9.7.3)
- Record body weight (see Section 9.7.4)
- Record vital signs (see Section 9.7.5)
- Perform 12-lead ECG (see Section 9.7.6)
- Take samples (hematology, HbA_{1c}, chemistry, urinalysis) for central laboratory evaluations (see Section 9.7.2.1).
Note: If HbA_{1c} cannot be analysed by the central laboratory due to technical reasons, subject can be considered suitable for randomization with one result only (Run-In or Screening).
- Record adverse events (see Section 9.6.1), accounting for the rules of assessment and documentation (see Section 9.6.1.3)
- Perform pregnancy test (see Section 9.6.2).

9.2.3 Visit 1 (randomization; Day 1 and baseline) - *amended*

This section was changed in Amendment 3, see Section 15.1.2.17.

All measurements on Visit 1 are to be performed on the day of the visit before first study drug intake. The following procedures and assessments will be performed at Visit 1:

- Instruct the subject on how to complete KDQOL-36 and EQ-5D-5L questionnaires; the subject completes the questionnaires (see Section 9.7.7).

- Obtain informed consent for sub-studies (see Section 9.7.8.1)
- Check inclusion and exclusion criteria (see Sections 6.1 and 6.2)
- Record use of concomitant medication (see Section 8.1)
- Record body weight (see Section 9.7.4)
- Record vital signs (see Section 9.7.5)
- Perform 12-lead ECG (see Section 9.7.6)
- Take samples (hematology, HbA_{1c}, chemistry, urinalysis) for central laboratory evaluations (see Section 9.7.2.1)
- Take samples (potassium, creatinine) for local safety laboratory evaluations (see Section 9.7.2.2)
- Optional: if the subject had signed informed consent for the sub-study, obtain respective samples for biomarkers (see Section 9.7.8.1.2) and/or iohexol clearance (see Section 9.7.8.1.3), perform echocardiography (see Section 9.7.8.1.1)
Note: Time window for the echocardiography at Visit 1 is -14/+7 days. On the day the echocardiography is performed, a blood sample should also be drawn to assess the echo biomarkers.
- Randomization to finerenone or placebo once daily (see Section 7.1)
- Dispense the study drug (see Section 7.2)
- Record adverse events (see Section 9.6.1), accounting for the rules of assessment and documentation (see Section 9.6.1.3)
- First administration of study drug.

9.2.4 Visit 2 (Month 1)

The following procedures and assessments will be performed at Visit 2:

- Record use of concomitant medication (see Section 8.1)
- Collect unused study drug and perform accountability to assess compliance (see Section 7.6)
- Dispense the study drug (see Section 7.2)
- Record body weight (see Section 9.7.4)
- Record vital signs (see Section 9.7.5)
- Take samples (limited chemistry) central laboratory evaluations (see Section 9.7.2.1)
- Take samples (potassium, creatinine) for local safety laboratory evaluations (see Section 9.7.2.2)
- Assess if the subject has any endpoint event(s) (see Table 13–1 and Section 9.6.1.3.1)

- Record adverse events (see Section 9.6.1), accounting for the rules of assessment and documentation (see Section 9.6.1.3).

9.2.5 Visit 3 (Month 4) - amended

This section was changed in Amendment 3, see Section 15.1.2.18.

Ideally, the study personnel should contact the subject prior to Visit 3 to remind them not to take the study drug as usual in the morning at home. The following procedures and assessments will be performed at Visit 3:

- Record use of concomitant medication (see Section 8.1)
- Collect unused study drug and perform accountability to assess compliance (see Section 7.6)
- Dispense the study drug (see Section 7.2)
- Record body weight (see Section 9.7.4)
- Record vital signs (see Section 9.7.5)
- Take samples (hematology, HbA_{1c}, chemistry, urinalysis) for central laboratory evaluations (see Section 9.7.2.1)
- Take samples (potassium, creatinine) for local safety laboratory evaluations (see Section 9.7.2.2)
- Obtain pre-dose sample for PK (see Section 9.5)
- Administer study drug after PK sample has been obtained (see Section 9.5)
- Optional: if the subject had signed informed consent for the sub-study, obtain respective samples for biomarkers (see Section 9.7.8.1.2) and/or iohexol clearance (see Section 9.7.8.1.3)
- Assess if the subject has any endpoint event(s) (see Table 13–1 and Section 9.6.1.3.1)
- Record adverse events (see Section 9.6.1), accounting for the rules of assessment and documentation (see Section 9.6.1.3).

9.2.6 Visit 4, 6, 7, 9, etc. (every 4 months; Month 8, 16, 20, 28, etc., excluding yearly visits) - amended

This section was changed in Amendment 3, see Section 15.1.2.19.

The following procedures and assessments will be performed at Visit 4, 6, 7, 9, etc.:

- Record use of concomitant medication (see Section 8.1)
- Collect unused study drug and perform accountability to assess compliance (see Section 7.6)
- Dispense the study drug (see Section 7.2)

- Record body weight (see Section 9.7.4)
- Record vital signs (see Section 9.7.5)
- Take samples (hematology, HbA_{1c}, chemistry) for central laboratory evaluations (see Section 9.7.2.1)
- Take samples (potassium, creatinine) for local safety laboratory evaluations (see Section 9.7.2.2)
- **Visit 4 only:** Obtain pre-dose sample for PK if no PK sample was taken at Visit 3 (see Section 9.5)
- Optional: if the subject had signed informed consent for the sub-study, obtain samples for iohexol clearance (see Section 9.7.8.1.3).
Note: Iohexol clearance should be performed every 8 months only (Visit 7, Visit 9, etc.)
- Assess if the subject has any endpoint event(s) (see Table 13–1 and Section 9.6.1.3.1)
- Record adverse events (see Section 9.6.1), accounting for the rules of assessment and documentation (see Section 9.6.1.3).

9.2.7 Visit 5, 8, 11, etc. (every 12 months; Month 12, 24, 36, etc.) - amended

This section was changed in Amendment 3, see Section 15.1.2.20.

The following procedures and assessments will be performed at Visit 5, 8, 11, etc.:

- Subject to complete KDQOL-36 and EQ-5D-5L questionnaires (see Section 9.7.7).
- Record use of concomitant medication (see Section 8.1)
- Collect unused study drug and perform accountability to assess compliance (see Section 7.6)
- Dispense the study drug (see Section 7.2)
- Perform physical examination (see Section 9.7.3)
- Record body weight (see Section 9.7.4)
- Record vital signs (see Section 9.7.5)
- Perform 12-lead ECG (see Section 9.7.6)
- Take samples (hematology, HbA_{1c}, chemistry, urinalysis) for central laboratory evaluations (see Section 9.7.2.1)
- Take samples (potassium, creatinine) for local safety laboratory evaluations (see Section 9.7.2.2)
- Obtain sample for PK (see Section 9.5)

- Optional: if the subject had signed informed consent for the sub-study, obtain samples for biomarkers (see Section 9.7.8.1.2), perform echocardiography (see Section 9.7.8.1.1)
- Optional: if the subject had signed informed consent for the sub-study, obtain samples for iohexol clearance (see Section 9.7.8.1.3).
Note: Iohexol clearance should be performed every 8 months only (Visit 5, Visit 11, etc.)
- Assess if the subject has any endpoint event(s) (see Table 13–1 and Section 9.6.1.3.1)
- Record adverse events (see Section 9.6.1), accounting for the rules of assessment and documentation (see Section 9.6.1.3)
- Perform pregnancy test (see Section 9.6.2).

9.2.8 Up-titration Visit (4 weeks \pm 7 days after up-titration or restart of study drug, and for up-titration of study drug) - amended

This section was changed in Amendment 3, see Section 15.1.2.21.

The following procedures and assessments will be performed at the Up-titration Visit (see Section 7.4 for details).

- Record use of concomitant medication (see Section 8.1)
- Collect unused study drug and perform accountability to assess compliance, if applicable (see Section 7.6)
- Record body weight (see Section 9.7.4)
- Record vital signs (see Section 9.7.5)
- Take samples (limited chemistry) central laboratory evaluations (see Section 9.7.2.1)
- Take samples (potassium, creatinine) for local safety laboratory evaluations (see Section 9.7.2.2)
- Assess if the subject has any endpoint event(s) (see Table 13–1 and Section 9.6.1.3.1)
- Record adverse events (see Section 9.6.1), accounting for the rules of assessment and documentation (see Section 9.6.1.3).

9.2.9 Premature Discontinuation (PD) Visit (as soon as possible but within 7 days after study drug is permanently discontinued) - amended

The section title was changed in Amendment 3, see Section 15.1.2.22.

If the PD visit cannot be performed within the timeframe specified, no PD visit is required. The following procedures and assessments will be performed at the PD Visit:

- The subject completes KDQOL-36 and EQ-5D-5L questionnaires (see Section 9.7.7)
- Record use of concomitant medication (see Section 8.1)
- Collect unused study drug and perform accountability to assess compliance (see Section 7.6)
- Perform physical examination (see Section 9.7.3)
- Record body weight (see Section 9.7.4)
- Record vital signs (see Section 9.7.5)
- Perform 12-lead ECG (see Section 9.7.6)
- Take samples (hematology, HbA_{1c}, chemistry) for central laboratory evaluations (see Section 9.7.2.1)
- Optional: if the subject had signed informed consent for the sub-study, obtain respective samples for biomarkers (see Section 9.7.8.1.2) and/or for iohexol clearance (see Section 9.7.8.1.3), perform echocardiography (see Section 9.7.8.1.1)
- Assess if the subject has any endpoint event(s) (see Table 13–1 and Section 9.6.1.3.1)
- Record adverse events (see Section 9.6.1), accounting for the rules of assessment and documentation (see Section 9.6.1.3).

9.2.10 End of study (EOS) visit - amended

This section was changed in Amendment 3, see Section 15.1.2.23.

The following procedures and assessments will be performed at the EOS Visit:

- The subject completes KDQOL-36 and EQ-5D-5L questionnaires (see Section 9.7.7)
- Record use of concomitant medication (see Section 8.1)
- Collect unused study drug and perform accountability to assess compliance (see Section 7.6)
- Perform physical examination (see Section 9.7.3)
- Record body weight (see Section 9.7.4)
- Record vital signs (see Section 9.7.5)
- Perform 12-lead ECG (see Section 9.7.6)

- Take samples (hematology, HbA1c, chemistry, urinalysis) for central laboratory evaluations (see Section 9.7.2.1)
- Optional: if the subject had signed informed consent for the sub-study, obtain respective samples for biomarkers (see Section 9.7.8.1.2) and/or for iohexol clearance (see Section 9.7.8.1.3), perform echocardiography (see Section 9.7.8.1.1)
- Assess if the subject has any endpoint event(s) (see Table 13–1 and Section 9.6.1.3.1)
 - Any eGFR declines that meet endpoint criteria that are identified at the EOS Visit, or that cannot be confirmed by the time of the EOS Visit, should be confirmed 4 weeks after the initial decline
- In exceptional circumstances only, if the subject is unable to attend this visit during the given timeframe, the subject (or primary physician / next of kin) should be contacted to obtain survival status.
- Record adverse events (see Section 9.6.1), accounting for the rules of assessment and documentation (see Section 9.6.1.3).

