The period between the subject's last intake of study drug and last visit in the study is referred to as the '*Follow-up Period*'. If a subject withdraws from study drug permanently but does not withdraw from the study, this would apply to the period between the Premature Discontinuation (PD) Visit, which should take place as soon as possible following permanent discontinuation of study drug, and the EOS Visit. In the case where a subject discontinues treatment at the EOS Visit, the Follow-up Period applies to the period between the EOS visit and PT visit.

All subjects who withdraw consent can be followed up for vital status if they do not sign the '*Declaration of Objection*' form. In addition, vital status can be obtained by the investigator from publicly available data sources. The collection of vital status must be obtained within the timelines provided by Bayer.

End of study

The end of the study as a whole will be reached as soon as the last visit of the last subject of Study 17530 has been reached in all centers in all participating countries (EU and non-EU).

The study will terminate either when:

- (1) the targeted number of primary efficacy endpoint events have been positively adjudicated
- OR
- (2) at a recommendation of the DMC, whichever is earlier.

After notification of study termination, for all subjects still participating in the study, an End-of-Study (EOS) Visit should be scheduled as soon as possible (within 4 weeks of notification at the latest) to determine whether the subject had an event for inclusion in the primary or secondary endpoints.

Subjects who are still on treatment will discontinue study drug treatment at the EOS Visit and must perform the Post-Treatment (PT) Visit (4 weeks + 5 days) after their last dose of study drug.

The primary completion event for this study is the last visit for the last subject.

The primary completion date for this study according to the FDA Amendment Act is specified in a separate document (not part of this study protocol).

6. Study population

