6.4 Withdrawal of subjects from study

6.4.1 Withdrawal

6.4.1.1 Discontinuation of study drug - *amended*

This section was changed in Amendment 3, see Section 15.1.2.6.

After randomization, discontinuation of **study drug** (for any reason) does not constitute the subject's withdrawal from the **study** (see also Section 6.4.1.2).

Study drug *must* be permanently discontinued if any of the following occurs:

- Pregnancy of the study subject (see also Section 9.6.2)

- The investigator is of the opinion that continuation of treatment with study drug is harmful to the subject's well-being
- The randomization code is broken by the investigator, or other responsible person, when knowledge of the subject's treatment is required
- Any investigational drug other than the study drug is used.

Study drug *may* be permanently discontinued if any of the following occurs:

- Any suspected drug-related AE or SAE
- If any exclusion criterion applies during treatment
- If a significant violation of the protocol occurs, as defined by the sponsor and the coordinating investigator.

In general, subjects who permanently discontinue study drug are expected to continue in the follow-up period and to attend all protocol-specified study visits, and should be encouraged to perform all assessments described in the visit schedule (see Section 9.2).

If a subject no longer on study drug is unable to attend the clinic for a study visit, a telephone consultation may be performed to determine if relevant health events / endpoints (e.g. development of CV or renal complications) have occurred. Ideally, a face-to-face visit should be performed at least once a year. Expected frequency of telephone contacts should be in line with the standard visit schedule, and therefore performed every 4 months. Ad hoc additional telephone contacts may also be requested (e.g. prior to the interim analysis) and made to the subject themselves or to other contact as provided by the patient, e.g. a next of kin, primary physician (or local equivalent).

Note that study drug may be temporarily discontinued (i.e. interrupted), as described in Section 7.4.

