9.1 Tabular schedule of evaluations - *amended*

This section was changed in Amendment 3, see Section 15.1.2.12 and Section 15.1.2.13.

Table 9–1 depicts the schedule of activities and evaluations for this study (17530).

An overview of the procedures for sub-studies of 17530 is provided in Table 9–2.

All randomized subjects will remain in the study until its termination, either:

- (1) after positive adjudication of the targeted number of primary efficacy endpoint events,
or
- (2) at a recommendation of the DMC.

Thus, all subjects, including those who stopped taking study drug, should be asked to attend all the protocol-specified study visits in order to perform all assessments as stipulated in the visit schedule (Table 9–1).

If any subject refuses to return for the defined assessments or is unable to do so, every effort should be made to contact him/her or a knowledgeable informant by telephone to ask if any of the primary, secondary, or other endpoints have been reached at the scheduled visits for the remaining duration of the study (see Section 6.4.1.1 for details). Attempts to contact the subject should be documented in the subject's records. If any subject refuses to be contacted by telephone (e.g. the subject withdrew consent to release further information), every effort should be made to obtain vital status (alive or dead) information through consultation of public databases, wherever allowed by local regulations.

Table 9–1 Study 17530: schedule of activities and evaluations - amended

Visit	Run-in	Screening	Visit 1 (Baseline)	Visit 2	Visit 3	Visit 4, 6, 7, 9, etc ^h	Visit 5, 8, 11, etc	Up-titration Visit ^j	PD Visit	EOS Visit ^k	PT Visit ^m
Day / Month	4 to 16 weeks pre-screening	≤ 2 weeks	Day 1	Month 1	Month 4	(every 4 months, i.e. Month 8, 16, 20, 28, etc)	(every 12 months, i.e. Month 12, 24, 36, etc)	For up-titration/restart after interruption, and for safety check 4 weeks ± 7 days after any up-titration (see also footnote j)	As soon as possible but within 7 days after SD is permanently discontinued	After study termination	4 weeks + 5 days after last SD intake
Informed consent	X										
In- and exclusion criteria	X	X	X								
Demographic data	X										
Smoking status	X										
Alcohol consumption	X										
Medical history	X										
Prior medication	X										
Concomitant medication	X	X	X	X	X	X	X	X	X	X	X
Randomization			X								
Drug accountability				X	X	X	X	X	X	X	
Study drug dispense			X	X	X	X	X				

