6.2 Efficacy

6.2.1 Analysis of primary efficacy variable

6.2.1.1 Primary efficacy variable: primary analysis

The primary efficacy variable is the time to first occurrence of the composite endpoint of CV death or non-fatal CV event (i.e. myocardial infarction, stroke, or hospitalization for HF). All events classifying for the primary endpoint have to be adjudicated positively by an independent adjudication committee.

The primary analysis of the primary efficacy variable will be performed in the FAS.

Events for inclusion in the primary analysis will be counted from the day of randomization (planned at Visit 1) onwards until the EOS visit following the study termination decision, or until the date of EOS notification + 4 weeks, if the EOS visit has not been performed. In the event of premature discontinuation from the study with no subsequent follow-up information, events will be counted up to the day of withdrawal from the study or non-CV death.

Randomized subjects without an event of the primary composite endpoint at the time of analysis will be censored at the date of their last contact up to and including the EOS visit or date of non-CV death. Subjects without any information about the primary composite endpoint after baseline will be censored at Day 1.

The hierarchical testing procedure which will be used for the primary and secondary efficacy variables is described in section [4.7](#).

In order to evaluate whether finerenone is superior to placebo in prolonging the time to the first event of the primary composite endpoint, the following null hypothesis will be tested using the logrank test at the two-sided significance level given above:

$$H_0: \lambda_{finerenone,k}(t) = \lambda_{placebo,k}(t) \text{ for all time points } t \geq 0 \text{ and each stratum } k$$

The alternative hypothesis will be:

$$H_1: \lambda_{finerenone,k}(t) \neq \lambda_{placebo,k}(t) \text{ for at least one time point } t \geq 0 \text{ and at least one stratum } k,$$

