6.2.2 Analysis of secondary efficacy variables

6.2.2.1 Secondary efficacy variables: primary analysis

Secondary efficacy variables are as follows:

- Time to first occurrence of the following renal composite endpoint:
 - onset of kidney failure, a sustained decrease of eGFR $\geq 40\%$ from baseline over at least 4 weeks, or renal death
- Time to all-cause hospitalization
- Time to all-cause mortality
- Change in UACR from baseline to Month 4
- Time to first occurrence of the following renal composite endpoint: onset of kidney failure, a sustained decrease in eGFR of $\geq 57\%$ from baseline over at least 4 weeks or renal death.

The primary analysis of the secondary efficacy variables will be conducted in the FAS.

See section 4.7 for the testing hierarchy for secondary endpoints and for multiplicity adjustment of significance levels.

The primary analysis of the secondary time-to-event endpoints will be conducted analogously to the primary analysis of the primary composite endpoint, with modifications to the

censoring rules as the events will differ. In the event of premature termination from the study with no subsequent follow-up information, subjects without any information about the composite endpoint after baseline will be censored at Day 1, and the following censoring rules will also apply:

- Renal events will be counted up to the day of the last visit when complete information on all components of the composite renal endpoint is available with an additional rule for events occurring after this visit. To account for events of kidney failure or renal death after the last eGFR is recorded at a clinic visit, such events will be included in the efficacy analysis if they occur in the period up to one day before the next planned clinic visit. This period would be a maximum of 5 months, given the next scheduled clinic visit should take place 4 months later, plus a time window for late attendance of one month. In addition, should the subject have a non-renal death in this period then the date of death will be used as the censoring date. Randomized subjects without an event of the renal composite endpoint at the time of analysis will be censored at the date of their last visit when complete information on all components of the composite renal endpoint is available, up to and including the EOS visit (should this visit satisfy this rule), or date of non-renal death using a time window of 5 months as above if a subsequent clinic visit had been planned.

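### The fallback contact for a missed EOS visit names survival status alone, conflicting with Protocol 9.1, and the SAP's undefined 'last contact' could count the unassessed interval as free of non-fatal events

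*Protocol*

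**What the plan says.** **Protocol 9.2.10 (EOS visit).** The fallback applies "In exceptional circumstances only, if the subject is unable to attend this visit during the given timeframe". In that case "the subject (or primary physician / next of kin) should be contacted to obtain survival status". Amendment 3 added this text for the EOS visit specifically.

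**Protocol 9.1.** For any subject who refuses or is unable to return, the site should telephone the subject or a knowledgeable informant "to ask if any of the primary, secondary, or other endpoints have been reached at the scheduled visits for the remaining duration of the study". Vital status alone is the next step down, for subjects who refuse telephone contact.

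**Protocol 6.4.1.1.** For subjects off study drug who cannot come to the clinic, "a telephone consultation may be performed to determine if relevant health events / endpoints" have occurred.

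**Protocol Section 5, End of study.** The EOS visit is held "to determine whether the subject had an event for inclusion in the primary or secondary endpoints".

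**SAP 6.2.1.1.** Subjects without a primary event "will be censored at the date of their last contact up to and including the EOS visit or date of non-CV death". Protocol 10.3.3.1 uses the last visit instead. If there is no EOS visit, the SAP counts events up to four weeks after the EOS notification.

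**SAP 6.2.2.1.** All-cause hospitalization is also censored at last contact. Subjects without a renal composite event are "censored at the date of their last visit when complete information on all components of the composite renal endpoint is available", with a limited extension for non-renal death. All-cause mortality is censored at the last date on which vital status was obtained.

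**The concern.** Two instructions cover the same telephone call and ask for different things. The EOS-specific one names only survival, and a site could reasonably take it as governing the final contact.

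The SAP then turns that contact into follow-up time. Nothing in 6.2.1.1 requires that non-fatal events were asked about at the last contact. A next of kin who confirms that the subject is alive has given full information for all-cause mortality and none on myocardial infarction, stroke or admission. Yet the call date can become the censoring date for all of them.

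At stake is the completeness of non-fatal event ascertainment between the last attended visit and the end of the study. This affects the primary endpoint and one secondary endpoint in the testing hierarchy.

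**Working it through.** **Step 1. Follow one subject.** Suppose the last attended visit is at time L, an infarction occurs one month later, and a survival-only call is made at L + 4 months (one visit interval).

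| Rule | Outcome for this subject |
|---|---|
| SAP 6.2.1.1, last contact read literally | No event; censored at L + 4 months; four unassessed months counted as event-free |
| Protocol 10.3.3.1, last visit | No event; censored at L; no unassessed time counted |
| Protocol 9.1 questions asked at the call | Event at L + 1 month, sent for adjudication |
| SAP tipping-point analysis (6.2.1.2, Appendix 9.1) | Imputes only for withdrawn consent or loss to follow-up, and only from last contact, here L + 4 months; the gap before it stays untouched |

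The window of notification plus four weeks decides which known events count. It does not make anyone ask.

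**Step 2. Reproduce the plan's event target.** Inputs from Protocol 10.4: hazard ratio 0.80, placebo event rate 8% per year, loss to follow-up 0.7% per year, finerenone discontinuation 5% per year with placebo hazard afterwards, 1:1 allocation, two-sided 5%, 90% power. A Markov (Lakatos-type) log-rank calculation with uniform accrual gives:

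| Accrual + last-subject follow-up | Events, plan / recomputed | Subjects, plan / recomputed |
|---|---|---|
| 33 + 11 months | 970 / 972 | 6212 / 6232 |
| 41 + 7 months | 976 / 979 | 6286 / 6305 |

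All four agree within 0.4%. The planning figures are not in question. At 90% power, 976 events correspond to a diluted hazard ratio of exp(−2 × (1.960 + 1.282) / √976) = 0.813.

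**Step 3. Size of the gap.** Unrecorded first events = N × share × (gap / 12) × non-fatal rate.

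- N = 7400 (SAP Section 3).
- Share of subjects alive with a survival-only contact: 0.5% to 5%. Assumed; the documents give no figure.
- Gap since the last endpoint enquiry: 1 to 5 months. Assumed, guided by four-monthly visits plus up to four weeks for scheduling EOS.
- Non-fatal first-event rate: 4% to 8% per year. Assumed. The planned placebo rate for the whole composite, CV death included, is 8%.

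| Case | Calculation | Events | Per cent of 976 |
|---|---|---|---|
| Low | 7400 × 0.005 × 1/12 × 0.04 | 0.12 | 0.01 |
| Middle | 7400 × 0.01 × 4/12 × 0.06 | 1.5 | 0.15 |
| High | 7400 × 0.05 × 5/12 × 0.08 | 12.3 | 1.26 |

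These figures put all 7400 subjects at risk. Removing the 976 who already have a first event scales them by (7400 − 976) / 7400 = 0.868, so the high case becomes 10.7. The unassessed time in the high case is 370 × 5/12 = 154 person-years.

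**Step 4. Power.** The study is stopped after about 976 events have been positively adjudicated, and EOS visits follow that notification. Events missed at EOS are therefore mostly additional to the target. Even if 12.3 were subtracted from it, power would be Φ(½ × √963.7 × 0.2075 − 1.960) = 89.6%, where 0.2075 is −ln of the diluted hazard ratio, against 90.0%.

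**The case against.** The other side has a good case on several points.

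- **Protocol 9.2.10 does not rule out endpoint questions.** A reader might infer that a subject who misses EOS is to be asked about survival and nothing else. The text does not say so: *only* qualifies the exceptional circumstances, not what is asked. Section 9.1 applies to every subject unable to return, for the rest of the study, and a site following both sections would ask. This stands. The defect is conflicting instructions, not a rule to forgo ascertainment.
- **The SAP separates its terms.** Mortality uses the date of vital status and hospitalization uses last contact, so the authors may have meant a contact that yields endpoint information. Subjects with no post-baseline information on the primary endpoint are censored at Day 1, which points the same way. That reading is plausible, but it is not written down. The renal rule shows that the SAP spells out the requirement where it wants it.
- **The pandemic is addressed.** SAP 6.2.4 says that most adjudicated events can still be collected without physical visits, and it plans re-censoring at pandemic onset. The re-censoring is supplemental and leaves the primary analysis as it is. The first argument depends on remote contacts asking about endpoints.
- **Affected shares of 10-20%.** A reader might infer these because the last study year overlapped the pandemic. No document supports them. The protocol calls the situation exceptional and plans for 0.7% annual loss to follow-up.

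**Conclusion.** The point holds as an inconsistency with a small consequence. Protocol 9.2.10 conflicts with 9.1 and with the stated purpose of EOS. The SAP's undefined last contact would let a survival-only call lengthen event-free follow-up for non-fatal primary events and hospitalizations. The tipping-point analysis does not reach that interval.

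Under the assumed ranges, about 0.1 to 12 first primary events could go unrecorded. The share of subjects drives the result and is unknown, and the estimate also assumes that sites follow 9.2.10 without 9.1. A reader might set 12 against 976 and see a shortfall. That does not follow, because the target is reached before EOS visits begin, so planned power is essentially unaffected. A reader might also infer a biased treatment comparison, but nothing in the documents suggests that the missed events would differ between arms.

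The reason to act is that better ascertainment costs very little, not that the trial's conclusion is at risk.

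**What to change.** **Protocol 9.2.10, or a site memo.** State that the fallback EOS contact asks the 9.1 questions as well as survival: every primary and secondary event and every hospitalization since the last enquiry, with suspected events and their source documents sent to the Clinical Event Committee.

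**SAP 6.2.1.1 and the hospitalization rule in 6.2.2.1.** Define the censoring date as the last contact, up to and including EOS, at which status for that endpoint was ascertained. A contact that yields vital status alone extends follow-up for all-cause mortality only. This applies the logic that the SAP already uses for the renal composites and for mortality. It also settles the difference from the protocol's last-visit rule, and the tipping-point imputation would then start where endpoint information ends.

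**Cost.** One sentence in each document and a few more questions on a call that is already required. The downside is slightly shorter censoring times for subjects from whom only vital status was obtained.
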